12.3.2. Serious Adverse Events

SAEs must be reported to the appropriate sponsor contact person by study-site personnel immediately, but no later than 24 hours of their knowledge of the event (Section 12.3.1).

Any ARI fulfilling the criteria of an SAE will be reported as such from vaccination on Day 1 and for the duration of the first RSV season (or 6 months after vaccination, whichever comes later), for the duration of the second RSV season, between the second and the third RSV season, and for the duration of the third RSV season. For participants in Revaccination Subcohorts, follow-up of ARIs will stop at the end of the second RSV season for Subcohort A, at the Day 730 (Month 24) visit for Subcohort B, and at the latest at the end of the third RSV season for Subcohort C. SAEs will not be updated after the RSV RT-PCR results become available and will remain listed on the eCRF as ARIs.

Information regarding SAEs will be transmitted to the sponsor using the Serious Adverse Event Form and Safety Report Form of the eCRF, which must be completed and reviewed by a physician from the study site, and transmitted to the sponsor immediately, but no later than 24 hours. The initial and follow-up reports of an SAE should be transmitted electronically or by facsimile (fax).

All SAEs that have not resolved by the end of the SAE reporting period, or that have not resolved upon discontinuation of the participant's participation in the study, must be followed until any of the following occurs:

- The event resolves
- The event stabilizes
- The event returns to baseline, if a baseline value/status is available
- The event can be attributed to agents other than the study intervention or to factors unrelated to study conduct
- It becomes unlikely that any additional information can be obtained (participant or health care practitioner refusal to provide additional information, lost to follow-up after demonstration of due diligence with follow-up efforts)

Suspected transmission of an infectious agent by a medicinal product will be reported as an SAE. Any event requiring hospitalization (or prolongation of hospitalization) that occurs during the course of a participant's participation in a study must be reported as an SAE, except hospitalizations for the following:

- Hospitalizations not intended to treat an acute illness or AE (eg, social reasons such as pending placement in long-term care facility)
- Surgery or procedure planned before entry into the study (must be documented in the eCRF). Note: Hospitalizations that were planned before the signing of the ICF, and where the underlying condition for which the hospitalization was planned has not worsened, will not be considered SAEs. Any AE that results in a prolongation of the originally planned hospitalization is to be reported as a new SAE.

The cause of death of a participant in a study during the entire study period, whether or not the event is expected or associated with the study vaccine, is considered an SAE and must be reported.

12.3.3. Pregnancy

All initial reports of pregnancy in partners of male participants must be reported to the sponsor by the study-site personnel within 24 hours of their knowledge of the event using the appropriate pregnancy notification form. Abnormal pregnancy outcomes (eg, spontaneous abortion, fetal death, stillbirth, congenital anomalies, ectopic pregnancy) are considered SAEs and must be reported using the Serious Adverse Event Form.

Follow-up information regarding the outcome of the pregnancy and any postnatal sequelae in the infant will be required.

12.3.4. Adverse Events of Special Interest

Adverse Events of Special Interest (AESIs) (including potential AESIs) are significant AEs that are judged to be of special interest because of clinical importance, known or suspected class effects, or based on nonclinical signals. AESIs (including potential AESIs) will be carefully monitored during the study by the sponsor.

AESIs (including potential AESIs) must be reported to the sponsor within 24 hours of awareness irrespective of seriousness (ie, serious and nonserious AEs) or causality following the procedure described above for SAEs.

AESIs must be reported using the AESI form in the eCRF using the eCRF completion guidelines.

Specific requirements for the AESI are described below.

12.3.4.1. Thrombosis with Thrombocytopenia Syndrome

As described in Section 1.1, TTS has been observed very rarely following vaccination with the Janssen COVID-19 vaccine and is considered to be an AESI in this study. TTS is a syndrome characterized by a combination of both a thrombotic event and thrombocytopenia.^{1,4}

Because this syndrome is very rare and not completely understood, all cases of thrombosis and/or thrombocytopenia should be reported to the sponsor within 24 hours of awareness using the AESI form. Each potential AESI will be reviewed to identify a vaccine-induced immune thrombotic thrombocytopenia (VITT) case. Responsibilities and procedures for identification, review, and evaluation of potential TTS cases are outlined in 2 separate charters: the thrombosis with thrombocytopenia syndrome Adjudication Committee (TTSAC) Charter and the 'Process of Case Assessment for TTS in the RSV Vaccine Interventional Clinical Studies Charter'. A potential TTS case is defined as:

- Thrombotic events: suspected deep vessel venous or arterial thrombotic events as detailed in [Attachment 13](#),
and/or
- Thrombocytopenia, defined as platelet count below 150,000 cells/mm³

Symptoms, signs, or conditions suggestive of a thrombotic event or thrombocytopenia should be recorded and reported as a potential AESI even if the final or definitive diagnosis has not yet been determined, and alternative diagnoses have not yet been eliminated or shown to be less likely. Follow-up information and final diagnoses, if applicable, should be submitted to the sponsor as soon as they become available.

In the event of thrombocytopenia, study site personnel should report the absolute value for the platelet count and the reference range for the laboratory test used.

For either a thrombotic event or thrombocytopenia, complete blood count including platelet count with a test for anti-PF4 and a coagulation profile should be provided as soon as possible upon the site becoming aware of the event. In case these results are not available at the time of the event report in the eCRF, the study site is recommended to obtain a complete blood count including platelet count and a coagulation profile (to be performed at the local laboratory). Repeat testing may be requested for confirmation upon sponsor discretion.

Aliquots of serum samples collected for immunogenicity tests can be reconverted for participant's safety purposes upon sponsor request ([Table 13](#)).

[Table 13](#) provides non-exhaustive list(s) of laboratory tests that may be performed (upon sponsor request).

In addition, the sponsor may request additional laboratory tests on additional blood samples obtained as soon as possible after the potential AESI onset, either during an ad hoc unscheduled visit or the next scheduled visit, whichever comes first. [Table 14](#) provides a non-exhaustive list of laboratory tests that may be requested by the sponsor in case of potential AESI reporting, for which additional samples may be needed.

Table 13: Laboratory Tests That May Be Performed Upon Sponsor Request on Immunogenicity Samples Collected on Days 1 and 15 After Potential AESI Reporting

Parameters	Timepoints

 Serum samples for assay such as but not limited to: 
 Heparin-Induced Thrombocytopenia (HIT)/PF4 Ab, IgG·(HIT assay) If the above test is positive, also consider: 
 Anti-cardiolipin antibody Beta-2 glycoprotein 	
 Days 1 and 15 visits (aliquots of serum samples collected for immunogenicity test can be reconverted for participant's safety purposes).

Note: results of the test should be reported in the narrative of the event and/or in the TTS AESI pages of the eCRF.

Table 14: Laboratory Tests That May Be Requested by the Sponsor to be Performed at the Central Laboratory After Potential AESI Reporting

Parameters	Timepoints

 • Serum/plasma/whole blood samples for coagulation-related assays such as but not limited to: 
 ◦ Fibrinogen ◦ D-dimer ◦ Lupus anticoagulant ◦ Anti-cardiolipin antibody ◦ Beta-2 glycoprotein ◦ Heparin-Induced Thrombocytopenia (HIT)/PF4 Ab, IgG (HIT assay) ◦ Platelet activation assay (if HIT/PF4 is positive) ◦ Homocysteine ◦ COVID-19 serological test 	
 • As soon as possible after the potential AESI onset upon sponsor request (during an ad hoc unscheduled visit or the next scheduled visit, whichever comes first).

Note: results of the test should be reported in the narrative of the event and/or in the TTS AESI pages of the eCRF. Irrespective on samples for central laboratory tests collection, relevant data for TTS assessment reported in the medical records of the participant should be reported in eCRF narrative of the event and/or in the TTS AESI pages of the eCRF.

AESIs (including potential AESIs) will require enhanced data collection and evaluation. Every effort should be made to report as much information as possible about the event to the sponsor in a reasonable timeframe. Relevant laboratory results can be entered on the AESI form in the eCRF, using the eCRF completion guidelines.

If the investigator is not the treating physician, every effort should be made to collect the information requested in the form from the treating physician and enter the available information in the eCRF.

If an event meets the criteria for an SAE (Section 12.1.1), it should be reported using the same process as for other SAEs.

Treatment and Follow-up Recommendation

The medical management of thrombotic events with thrombocytopenia is different from the management of isolated thromboembolic diseases. Study site personnel and/or treating physicians should follow available guidelines for treatment of thrombotic thrombocytopenia (eg, American Society of Hematology 2022¹; British Society of Haematology 2022⁵; CDC 2021⁶). The use of heparin may be harmful and alternative treatments may be needed. Consultation with a hematologist is strongly recommended.

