- w. All SAEs will be reported from administration of study vaccine on Day 1 until the end of the first RSV season (or 6 months after vaccination, whichever comes later) and from revaccination on Day 365 until the end of the second RSV season (or 6 months after revaccination, whichever comes later). All SAEs and AESIs (including potential AESIs) will be reported from revaccination on Day 730 until 6 months after revaccination. In addition, SAEs classified as related to the study vaccine, SAEs resulting in death, (S)AEs resulting in study discontinuation and (S)AEs resulting from procedures and non-investigational (concomitant) Janssen products will be collected during the participant's entire study participation. Note: refer to footnote [cc](#) for SAEs related to ARIs.
- x. Only applicable from the time of local approval of protocol amendment 6.
- y. Concomitant medications will be collected for all participants when associated with an SAE or AESI. Note: refer to footnote [w](#) for the SAEs and AESIs collected during the RSV season.
- z. On Day 365/Day 730, changes in the use of any concomitant medication since the last visit should be recorded (refer to Section 8).
- aa. Aliquots of serum samples collected for immunogenicity tests can be reconverted for participant's safety purposes upon sponsor request. Please refer to [Table 13](#) for a non-exhaustive list of tests that may be requested to be performed on these samples in case of potential AESI reporting.
- bb. Concomitant medications will be collected from the time of revaccination through the following 28 days. Other concomitant medications will be collected only when associated with any SAE or AESI.
- cc. ARI surveillance will be via the eDiary which participants must complete at least twice weekly. Procedures in the event of an ARI are described in the [Schedule of Activities – Assessments for Participants with an ARI Episode](#). Collection of SAEs associated with ARIs and complications related to ARIs that classify as SAEs will stop at the end of the second RSV season.
- dd. Each study participant will be invited to complete an IEC/IRB approved Experience Survey, to share his/her experience as a volunteer in this study. The responses will be collected by an external party and anonymously provided to the sponsor.
- ee. The Day 730 visit should take place no later than by the end of November 2021.

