- o. Participants will be re-trained on how to use the eDiary, if needed, and on how to collect a midturbinate nasal swab, if applicable.
- p. To include Inclusion Criteria 1, 7, 8, and 9 and Exclusion Criteria 7, 11, 14.2, 17, and 18.
- q. To include Inclusion Criteria 5.1, 6, and 7 and Exclusion Criteria 1, 2, 4, 12, 13, 14.2, 20.1, 21.1 and 22.
- r. Participants may be provided a new nasal swab kit in case of expiration of their current kit.
- s. All participants will be closely observed for a minimum of 30 minutes post-revaccination. Any unsolicited, solicited local and systemic AEs will be documented by study-site personnel following this observation period. Vital signs (body temperature, blood pressure, heart rate, respiratory rate, and oxygen saturation) will be

obtained at the end of the observation period. Any clinically relevant abnormalities must be recorded on the AE page of the eCRF. Actual values (normal and abnormal) will only be documented in the eCRF for body temperature.

- t. Participants will be re-randomized in a 1:1:1 ratio to revaccination with Ad26.RSV.preF alone, RSV preF protein alone, or Ad26.RSV.preF/RSV preF protein. Refer to [Table 2](#) and [Figure 5](#)/[Figure 6](#).
- u. Solicited local and systemic AEs will be collected from vaccination until 7 days after vaccination. If a solicited AE has not resolved 7 days post-vaccination, it will continue to be followed-up until the event has returned to baseline.
- v. All AEs and special reporting situations related to study procedures or to non-investigational (concomitant) Janssen products will be reported from ICF signature onwards until the end of the participant's study participation. All other AEs (unsolicited) and special reporting situations will be reported from revaccination through the following 28 days.
- w. All SAEs will be reported from administration of study vaccine on Day 1 until the end of the first RSV season (or 6 months after vaccination, whichever comes later), and all SAEs and AESIs (including potential AESIs) will be reported from revaccination on Day 730/Day 1,095 until 6 months after revaccination. In addition, SAEs classified as related to the study vaccine, SAEs resulting in death, (S)AEs resulting in study discontinuation and (S)AEs resulting from procedures and non-investigational (concomitant) Janssen products will be collected during the entire study. Note: refer to footnote [bb](#) for SAEs related to ARIs.

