- x. Concomitant medications will be collected for all participants when associated with an SAE or AESI. Note: refer to footnote [w](#) for the SAEs and AESI collected during the RSV season.
- y. On Day 365/Day 730/Day 1,095, changes in the use of any concomitant medication since the last visit should be recorded (refer to Section 8).
- z. Aliquots of serum samples collected for immunogenicity tests can be reconverted for participant's safety purposes upon sponsor request. Please refer to [Table 13](#) for a non-exhaustive list of tests that may be requested to be performed on these samples in case of potential AESI reporting.
- aa. Concomitant medications will be collected from the time of revaccination through the following 28 days. Other concomitant medications will be collected only when associated with any SAE or AESI.
- bb. ARI surveillance will be via the eDiary which participants must complete at least twice weekly. Procedures in the event of an ARI are described in the [Schedule of Activities – Assessments for Participants with an ARI Episode](#). Collection of SAEs associated with ARIs and complications related to ARIs that classify as SAEs will stop on Day 730.
- cc. Each study participant will be invited to complete an IEC/IRB approved Experience Survey, to share his/her experience as a volunteer in this study. The responses will be collected by an external party and anonymously provided to the sponsor.
- dd. The Day 730 visit should take place no later than by the end of November 2021.
- ee. When the window for the end of season visit at the end of the NH RSV season is not coinciding with at least 6 months SAE or AESI follow-up, a separate SAE or AESI safety follow-up call should be conducted 6 months after revaccination and captured as an unscheduled visit.

AE=adverse event, AESI=adverse event of special interest, ARI=acute respiratory infection, d=day, eCRF=electronic Case Report Form, IADL=Instrumental Activities of Daily Living, ICF=informed consent form, IEC/IRB=Independent Ethics Committee/Institutional Review Board, mo=month, MRU=Medical Resource Utilization, NH=Northern Hemisphere, PGI-H=Patient Global Impression of Health, RiiQ=Respiratory Infection Intensity and Impact Questionnaire (RiiQ™) v2 (2018), RSV=respiratory syncytial virus, SAE=serious adverse event, SARS-CoV-2=Severe Acute Respiratory Syndrome Coronavirus-2, vac=vaccination, we=week

SCHEDULE OF ACTIVITIES – REVACCINATION SUBCOHORTS 1C AND 2C (N=240)*

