- u. All participants will be closely observed for a minimum of 30 minutes post-revaccination. Any unsolicited, solicited local and systemic AEs will be documented by study-site personnel following this observation period. Vital signs (body temperature, blood pressure, heart rate, respiratory rate, and oxygen saturation) will be obtained at the end of the observation period. Any clinically relevant abnormalities must be recorded on the AE page of the eCRF. Actual values (normal and abnormal) will only be documented in the eCRF for body temperature.
- v. Solicited local and systemic AEs will be collected from vaccination until 7 days after vaccination. If a solicited AE has not resolved 7 days post-vaccination, it will continue to be followed-up until the event has returned to baseline.
- w. All AEs and special reporting situations related to study procedures or to non-investigational (concomitant) Janssen products will be reported from ICF signature onwards until the end of the participant's study participation. Note that for the time period between the last end of the RSV season visit and the revaccination, the aforementioned AEs and special reporting situations will be collected retrospectively upon the day of revaccination. All other AEs (unsolicited) and special reporting situations will be reported from revaccination through the following 28 days.
- x. All SAEs will be reported from administration of study vaccine on Day 1 until the end of the first RSV season (or 6 months after vaccination, whichever comes later), and all SAEs and AESIs (including potential AESIs) will be reported from revaccination on Day 1,095 until 6 months after revaccination. Note: refer to footnote [dd](#) for SAEs related to ARIs.
- y. SAEs classified as related to the study vaccine, SAEs resulting in death, (S)AEs resulting in study discontinuation and (S)AEs resulting from procedures and non-investigational (concomitant) Janssen products will be collected during the participant's entire study participation. Note that for the time period between the last end of the RSV season visit and the revaccination these (S)AEs will be collected retrospectively upon the day of revaccination.
- z. Concomitant medications will be collected for all participants when associated with an SAE or AESI. Note: refer to footnote [x](#) for the SAEs and AESIs collected during the RSV season.

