For all Revaccination Subcohorts, SAEs classified as related to the study vaccine, SAEs resulting in death, (S)AEs leading to discontinuation from the study, and (S)AEs and special reporting situations related to study procedures or to non-investigational (concomitant) Janssen products will be collected during the entire study for all participants. For the participants in the Revaccination Subcohort C, these (S)AEs will be collected retrospectively for the time period between the last end of the RSV season visit and the revaccination upon the day of revaccination.

From the time of local approval of protocol amendment 6 onwards, TTS is considered to be an AESI. Thrombotic events and/or thrombocytopenia (defined as platelet count below 150,000 cells/mm³) are considered to be potential AESIs. All AESIs, including potential AESIs, will be reported to the sponsor from the moment of revaccination until 6 months after revaccination.

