- During the entire study, (S)AEs and special reporting situations related to study procedures or to non-investigational (concomitant) Janssen products will be reported from the time a signed and dated informed consent form (ICF) is obtained onwards until the end of the study period for each participant.

The (S)AE listing in the eCRF will not be updated based on the RSV RT-PCR results and will remain listed on the eCRF as ARIs.

For Revaccination Subcohort A, all SAEs will be reported from administration of study vaccine on Day 1 until the end of the first RSV season (or 6 months after vaccination, whichever comes later), and from the time of revaccination at Month 12 until the end of the second RSV season, or until 6 months after revaccination, whichever comes later. For Revaccination Subcohort 2A, all SAEs and AESIs will also be collected from the time of revaccination on Day 730 until 6 months after revaccination. For Revaccination Subcohorts B and C, all SAEs and AESIs will be collected from the time of revaccination until 6 months thereafter. Collection of SAEs associated with ARIs and complications related to ARIs that classify as SAEs will stop at the end of the second RSV season for Subcohort A, on Day 730 (Month 24) for Subcohort B, and at the latest at the end of the third RSV season for Subcohort C.

For all Revaccination Subcohorts, SAEs classified as related to the study vaccine, SAEs resulting in death, (S)AEs leading to discontinuation from the study, and (S)AEs and special reporting situations related to study procedures or to non-investigational (concomitant) Janssen products will be collected during the entire study for all participants. For the participants in the Revaccination Subcohort C, these (S)AEs will be collected retrospectively for the time period between the last end of the RSV season visit and the revaccination upon the day of revaccination.

From the time of local approval of protocol amendment 6 onwards, TTS is considered to be an AESI. Thrombotic events and/or thrombocytopenia (defined as platelet count below 150,000 cells/mm³) are considered to be potential AESIs. All AESIs, including potential AESIs, will be reported to the sponsor from the moment of revaccination until 6 months after revaccination.

The sponsor will evaluate any safety information that is spontaneously reported by an investigator beyond the time frame specified in the protocol.

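### The stored sera named for TTS-related antibody testing (Days 1 and 15) predate every AESI-monitored revaccination by about 2 or 3 years, so they offer a remote baseline but no post-dose result

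*Protocol*

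**What the plan says.** **Which stored sera may be tested.** Section 12.3.4.1 allows serum taken for immunogenicity to be diverted to safety testing: "Aliquots of serum samples collected for immunogenicity tests can be reconverted for participant's safety purposes upon sponsor request". Table 13 then fixes which sera. Its title is "Laboratory Tests That May Be Performed Upon Sponsor Request on Immunogenicity Samples Collected on Days 1 and 15 After Potential AESI Reporting", and its time-point column reads "Days 1 and 15 visits (aliquots of serum samples collected for immunogenicity test can be reconverted for participant's safety purposes". The tests are a HIT/PF4 antibody assay and, if that is positive, anti-cardiolipin antibody and beta-2 glycoprotein.

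The same permission appears as a footnote in the schedules for Cohort 1 (cc), 1A (aa), 2A (aa), 1B (y), 2B (z) and 1C/2C (bb). On the humoral-sample row of each, the marker sits on the Day 1 and Day 15 samples and on no later one.

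**When potential AESIs are collected.** Section 12.3.1 states: "From the time of local approval of protocol amendment 6 onwards, TTS is considered to be an AESI". Section 9.2.4.1 sets the window: "All AESIs, including potential AESIs, will be reported to the sponsor from the moment of revaccination until 6 months after revaccination". The schedules make it specific:

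- 2A, footnote w: "All SAEs and AESIs (including potential AESIs) will be reported from revaccination on Day 730 until 6 months after revaccination"
- 1B, footnote v: from the Day 730 revaccination, for 6 months
- 2B, footnote w: all SAEs and AESIs "will be reported from revaccination on Day 730/Day 1,095 until 6 months after revaccination"
- 1C and 2C, footnote x: "all SAEs and AESIs (including potential AESIs) will be reported from revaccination on Day 1,095 until 6 months after revaccination"

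The Cohort 1 and 1A schedules carry the serum footnote but have no AESI row.

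**The concern.** The reason to keep serum from before and after a dose is that a pair can separate antibody already present from antibody that appeared after that dose. Table 13 names a pair that surrounds the first injection, while the events it serves are collected only after a later one. For participants who started on placebo, the named pair surrounds an injection with no active vaccine in it.

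At stake is how a stored-sample result can be interpreted. A negative Day 1/Day 15 pair says nothing about an antibody response to the revaccination. A positive one would show only that antibody was present 2 or 3 years before that dose. The sera that bear directly on the question are drawn under the same protocol but are not named.

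**Working it through.** No sample size, power or alpha is involved, and the protocol gives no figure to reproduce. The check sets the sample days beside the AESI windows, using nominal visit days.

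**1. Does Day 15 mean 14 days after any dose?** Not as written. Table 13 refers to visits, and the schedules number the 14-day post-revaccination visits 744 and 1,109. Where the protocol wants a dose-relative Day 15 (Sections 11.2.4 and 11.9.2), it says which vaccination it follows.

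**2. Gap from the named sera to the start of the AESI window.** Gap = revaccination day − sample day.

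| Monitored dose | Subcohorts (planned N) | From Day 1 | From Day 15 |
|---|---|---|---|
| Day 730 | 2A third (120), 1B second (135), 2B second (135) | 730 − 1 = 729 | 730 − 15 = 715 |
| Day 1,095 | 2B third (135), 1C second (120), 2C second (120) | 1,095 − 1 = 1,094 | 1,095 − 15 = 1,080 |

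Taking 6 months as 183 days, the gap from Day 15 to the end of the window is 730 + 183 − 15 = 898 days, or 1,095 + 183 − 15 = 1,263 days.

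**3. How many planned doses are concerned.** Day 730: 120 + 135 + 135 = 390. Day 1,095: 135 + 120 + 120 = 375. Total: 390 + 375 = 765. Group 2 share: 120 + 135 + 135 + 120 = 510, and 510/765 = 66.7%. In all 510 the named sera predate any active vaccine. For none of the 765 is either named serum a post-dose sample.

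**4. Sera the schedules already collect inside the window.**

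- Day 730 dose in 2A, 1B and 2B: Days 730 (pre-dose), 737, 744, 758, 814, 898
- Day 1,095 dose in 2B: Days 1,095 (pre-dose), 1,102, 1,109, 1,123, 1,179, 1,263
- Day 1,095 dose in 1C and 2C: Days 1,095 (pre-dose), 1,109, 1,179, 1,263. There is no 7-day visit, and the 28-day contact has no draw.

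So a pre-dose and a 14-day sample exist in every AESI-monitored subcohort. Section 1.1 puts symptom onset with the other Ad26 vaccine at roughly 1 to 2 weeks after vaccination, a period those two samples span.

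**The case against.** The strongest reply is that diagnosis does not depend on Table 13. Section 12.3.4.1 asks for a blood count, anti-PF4 test and coagulation profile as soon as possible after the site learns of an event. Table 14 allows fresh samples and repeats every assay in Table 13. Stored-serum testing is optional and at the sponsor's request, and case review falls under two charters that are not at hand. This stands, and it limits the severity. A reader might infer that the whole TTS work-up fails, and the protocol does not support that. Event-time testing still leaves a gap, because a sample taken only after the event cannot tell earlier antibody from antibody that followed the revaccination. Table 14 sampling is also on request and may wait for the next scheduled visit.

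A reader might also infer that the named sera are useless. They are not: the Day 1 serum predates any study vaccine and can show pre-existing anti-PF4 antibody.

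A third tempting reading is that the gap runs from 1 to 3 years. The general sentence in Section 9.2.4.1 has no lower limit, and a Month 12 dose would give 365 − 15 = 350 days. But the 1A schedule has no AESI row, and footnote w for 2A starts collection at Day 730. The interval is about 2 or 3 years.

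The description of the list as non-exhaustive does not cure the mismatch, since it qualifies the tests and not the time points. It is fair to add that the footnote wording itself sets no day limit, that nothing expressly forbids using later sera, and that the 2B markers are not wholly reliable: one concomitant-medication row there carries the serum footnote's letter. The day limit therefore rests mainly on Table 13, which is explicit.

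**Conclusion.** The inconsistency is real and moderate. Table 13 ties stored-serum testing to two visits that precede every AESI-monitored dose. The Day 15 sample does so by a nominal 715 or 1,080 days, and for two thirds of the planned monitored doses both samples surround placebo. The pair gives a remote baseline and cannot show a response to the revaccination.

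The 765 doses measure how general the mismatch is, not how many work-ups are affected. Only participants with a potential AESI for whom the sponsor requests stored-serum testing are touched, and the protocol gives no expected number. Of the 765, 240 belong to Subcohort C, which was conditional on Subcohort B results.

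Timing narrows the practical reach. The amendment log places the laboratory-test language in Amendment 8 (February 2023), and Day 730 visits were due by the end of November 2021, so the 6-month windows after those doses had already closed. The doses that could still be in their window were the Day 1,095 ones (375 planned), which have the longer gap.

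The conclusion assumes nominal visit days, AESI windows as in the subcohort schedules, and Days 1 and 15 read as the numbered visits.

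**What to change.** Reconcile the title and time-point column of Table 13, and the matching footnotes in the schedules, with the AESI window. The stored sera eligible for testing should include the pre-dose sample on the day of the revaccination preceding the potential AESI and the scheduled samples after it: 14 days in all AESI-monitored subcohorts, and 7 and 28 days only in 2A (third vaccination) and Subcohort B. Days 1 and 15 should stay as an early reference. The footnote markers should move with the text, and its place in the Cohort 1 and 1A schedules, which have no AESI row, should be settled at the same time.

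The change is to the wording of one table and a set of footnotes. It needs no new visit or blood draw. The small downside is that some immunogenicity serum would be used up in the few participants with an event.
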